#### Sex

- 6. Male or female participant.
- 7. Female participants of childbearing potential and male participants must follow protocol-specified contraception guidance (Section 10.5.2).

### **Informed Consent**

8. Capable of giving signed informed consent as described in Section 10.1.3, which includes compliance with the requirements and restrictions listed in the ICF and in this protocol.

#### **Other Inclusions**

9. Vaccinated against meningococcal infection (*Neisseria meningitidis*) within 3 years prior to, or at the time of, randomization (Day 1).

Participants who initiate study intervention less than 2 weeks after receiving a meningococcal vaccine must receive appropriate prophylactic antibiotics until at least 2 weeks after the vaccination against *N meningitidis*.

# 5.2. Exclusion Criteria

A participant will be excluded from the study if any exclusion criteria are satisfied.

### **Medical Conditions**

- 1. Any medical condition (eg, cardiac, pulmonary, renal, oncologic, or psychiatric) that, in the opinion of the Investigator or the Medical Monitor, might interfere with participation in the study, pose any added risk to the participant, or confound the assessment of the participant.
- 2. History of thymectomy, thymomectomy, or any other thymic surgery within 12 months prior to the Screening Visit.
- 3. Any untreated thymic malignancy, carcinoma, or thymoma.

Participants with a history of treated thymic malignancy or carcinoma are eligible for enrollment if they meet the following conditions:

- a. Treatment completed > 5 years prior to the Screening Visit
- b. No known recurrence within the 5 years prior to the Screening Visit
- c. No radiological indication of recurrence in a computed tomography (CT) or magnetic resonance imaging (MRI) scan, including administration of IV contrast, performed within 6 months of randomization (Day 1)

Participants with a history of treated benign thymoma are eligible if they meet the following conditions:

d. Histopathological or equivalent records indicating the diagnosis of benign thymoma

- e. Treatment completed > 12 months prior to the Screening Visit
- f. No known recurrence within the 12 months prior to the Screening Visit
- g. No radiological indication of recurrence in a CT or MRI scan, including administration of IV contrast, performed within 6 months of randomization (Day 1)
- h. If adequate records confirming the diagnosis of benign thymoma are not available, the participant must satisfy the eligibility criteria for thymic malignancy or carcinoma stated above.

Thymomas classified as  $\leq$  Stage II according to the Masaoka Staging System are considered benign; thymomas classified as  $\geq$  Stage III are considered malignant (Detterbeck, 2014; Masaoka, 2010).

- 4. Clinical features that, in the opinion of the Investigator, are consistent with Clinical Deterioration of MG at the time of the Screening Visit or at any time during the Screening Period prior to randomization (Day 1).
- 5. History of seizure.
- 6. History of *N* meningitidis infection.
- 7. Evidence of human immunodeficiency virus (HIV antibody positive) infection at the Screening Visit.
- 8. History of hypersensitivity to any ingredient contained in the study intervention.
- 9. Known or suspected history of drug or alcohol abuse or dependence within 1 year prior to the Screening Visit.
- 10. Evidence of hepatitis B (hepatitis B positive hepatitis surface antigen [HbsAg] or positive hepatitis B core antibody [anti-HBc]) with negative surface antibody [anti-HBs] or hepatitis C viral infection (hepatitis C virus [HCV] antibody positive, except for patients with documented successful treatment and documented sustained virologic response [SVR]) at Screening.
- 11. History of malignancy within 5 years of the Screening Visit, with the exception of nonmelanoma skin cancer or carcinoma in situ of the cervix that has been treated with no evidence of recurrence.
- 12. History of persistent or recurrent infections prior to the Screening Visit.
- 13. Active systemic bacterial, viral, or fungal infection within 14 days prior to study intervention administration on Day 1.
- 14. Presence of fever as documented by a temperature  $\geq 38^{\circ}$ C (100.4°F) within 7 days prior to administration of study intervention on Day 1.
- 15. History or presence of any risk factors for Torsades de Pointes (eg, heart failure/cardiomyopathy or family history of Long QT Syndrome), a screening QT interval corrected using Fridericia's formula (QTcF) > 450 msec for males and > 470 msec for females, or receiving medications known to significantly increase the corrected QT interval (QTc).
- 16. Laboratory abnormalities at the Screening Visit, including:
  - a. Alanine aminotransferase  $> 2 \times$  the upper limit of normal (ULN)

- b. Direct bilirubin  $> 2 \times ULN$
- 17. Estimated glomerular filtration rate (eGFR) < 30 mL/min/1.73 m^2 and/or are on dialysis.
- 18. Any other clinically significant laboratory abnormality that, in the opinion of the Investigator, would make the participant inappropriate for the study or put the participant at undue risk.

### **Prior/Concomitant Therapy**

19. Use of the following within the time periods specified below:

- a. IVIg or subcutaneous immunoglobulin (SCIg) within the 4 weeks (28 days) prior to the Screening Visit
- b. Use of PE and PP within the 4 weeks (28 days) prior to the Screening Visit
- c. Use of rituximab within the 6 months (180 days) prior to the Screening Visit
- d. Use of tacrolimus or cyclosporine within the 4 weeks (28 days) prior to the Screening Visit
- 20. Any previous or current treatment with complement inhibitors (eg, eculizumab, ravulizumab).
- 21. Use of known cytochrome P450, family 3, subfamily A (CYP3A) sensitive substrates, moderate or strong CYP3A inducers, and/or moderate or strong CYP3A inhibitors from 2 weeks or 5 half-lives, whichever is longer, prior to the first administration of study intervention on Day 1 (randomization) (full list provided in Table 13).
- 22. Use of selected medications known to lower the seizure threshold and/or cause seizure (full list provided in Section 10.11).
- 23. Current treatment with a biologic medication that may affect immune system functioning or has stopped treatment with a biologic medication that may affect immune system functioning, and 5 terminal half-lives of the biologic medication have not elapsed by the time of the Screening Visit. Participants receiving prior treatment with an FcRn inhibitor ≥ 5 half-lives before the Screening Visit may be enrolled but the total immunoglobulin G (IgG) level must be above the lower limit of normal (LLN) before these participants can be randomized.

#### **Prior/Concurrent Clinical Study Experience**

24. Participation in another interventional treatment study or use of any experimental therapy within 30 days before the Screening Visit or within 5 half-lives of the study intervention, whichever is greater.

#### **Other Exclusions**

- 25. Pregnant, breastfeeding, or intending to conceive during the course of the study.
- 26. Inability to travel to the clinic for specified visits or fulfill the logistical requirements of study intervention administration.
- 27. Planned surgical procedure during the course of the study.

# **5.3.** Lifestyle Considerations

#### 5.3.1. Medications

If a participant is taking a cholinesterase inhibitor, the dose must be withheld for at least 8 hours prior to the QMG assessment at time points presented in the SoA (Section 1.3).

### 5.3.2. Meals and Dietary Restrictions

Certain foods such as grapefruit have been shown to be inhibitors of CYP3A4 enzyme activity. Participants should refrain from consuming these foods and beverages from 2 weeks prior to the first administration of study intervention on Day 1 (randomization) until 2 weeks after the final dose of study intervention.

# 5.4. Screen Failures

Screen failures are defined as participants who consent to participate in the clinical study but are not subsequently randomized. A minimal set of screen failure information is required to ensure transparent reporting of screen failure participants to meet the Consolidated Standards of Reporting Trials publishing requirements and to respond to queries from regulatory authorities. Minimal information includes demography, screen failure details (eg, failed eligibility criteria), and any adverse events (AEs), including any serious adverse events (SAEs) and any related concomitant medication, occurring during the Screening Period.

Individuals who do not meet the criteria for participation in this study (screen failure) due to a reason that is expected to resolve, or has resolved, may be rescreened based on discussion and agreement between the Investigator and the Medical Monitor.

# 6. STUDY INTERVENTION

Study intervention is defined as any investigational intervention(s), marketed product(s), placebo, or medical device(s) intended to be administered to a study participant according to the study protocol.

# 6.1. Study Intervention(s) Administered

- ALXN2050 drug product will be provided as tablets that are manufactured using a common blend.
  - The 60 mg formulation will be used in Study ALXN2050-MG-201.
- Matching placebo will be manufactured in the same fashion, without the active ingredient. ALXN2050 and placebo tablets will be identical in appearance.
- The participant will be provided with sufficient study intervention to last until their next study visit. Additional details will be provided in the interactive response technology (IRT) manual.
- In order to maintain the study blind for participants, Investigators, and site personnel, each of the 2 daily doses will consist of 3 tablets that in combination correspond to the assigned treatment group.
  - 180 mg: three 60 mg tablets
  - 120 mg: two 60 mg tablets and one placebo tablet
  - Placebo: 3 placebo tablets
- During in-clinic visits, the participant will be administered the first dose of study intervention. The second dose of study intervention is to be taken at home. Whether in the clinic or at home, the timing of administration should be consistent.
- In the event of a missed dose, the participant should be instructed to take the study intervention within 6 hours of the originally scheduled time. If more than 6 hours have passed, the missed dose should be skipped. In either scenario, the next dose should be taken according to the original dosing schedule.

The specific details of study intervention are presented in Table 8.

#### Table 8: Study Intervention

Study Intervention Name	ALXN2050 (Formerly ACH-0145228)	Placebo
Dose formulation	tablet	tablet
Unit dose strength(s)	60 mg	NA
Dose level(s) and frequency	120 mg bid or 180 mg bid	bid
Route of administration	oral	oral
IMP or AxMP	IMP	IMP
Sourcing	Alexion Pharmaceuticals, Inc.	Alexion Pharmaceuticals, Inc.

Abbreviations: AxMP = auxiliary medicinal product; bid = twice daily; IMP = investigational medicinal product; NA = not applicable

#### 6.1.1. Study Intervention(s) Packaging and Labeling

Study intervention will be provided in tamper-proof containers that will be labeled according to country-specific regulations. At a minimum, the container will be labeled with:

- The protocol number
- Lot number/expiry date
- Alexion name and address
- Instructions for use and storage

#### 6.1.2. Optional Dosing eDiary Tool

Participants will be provided with an optional dosing eDiary tool which is to be used as a reminder for taking the assigned study intervention throughout the duration of the study. Participants are advised to enter the date on which the assigned study treatment is scheduled and mark the chart each time the morning and evening dose is taken. As this is an optional tool, there will be no collection of data either by Alexion or the Investigator's site (ie, it will not be used for study intervention accountability).

### 6.2. Preparation/Handling/Storage/Accountability

#### 6.2.1. Preparation

The study intervention will be provided by Alexion; therefore, no specific preparation instructions are required.

#### 6.2.2. Storage and Handling

• Study intervention must be stored in the containers as provided at 15°C to 30°C. Participants should be instructed to keep their study medications in the original container at room temperature at home.

- Study intervention will be shipped directly to each investigational site. When the medication is stored at the investigational site, the Investigator or designee must confirm appropriate temperature conditions have been maintained during transit (a temperature monitor will accompany each shipment) for all study intervention received and that any discrepancies are reported and resolved before dispensation and use of the study intervention.
- Only participants enrolled in the study may receive the study intervention and only authorized site staff may supply or administer the study intervention. When the medication is stored at the investigational site, all study intervention must be stored in a secure, environmentally controlled, and monitored (manual or automated) area in accordance with the labeled storage conditions with access limited to the Investigator and authorized site staff.

#### 6.2.3. Accountability and Disposal

- The Investigator, institution, or the head of the medical institution (where applicable) is responsible for study intervention accountability, reconciliation, and record maintenance (ie, receipt, reconciliation, and final disposition records).
  - This responsibility includes the reporting of any temperature excursions and product complaints to [contact] and [contact] within 1 business day of awareness.

A product complaint is defined as any written, electronic, or oral communication that alleges deficiencies related to the identity, quality, durability, reliability, usability, safety, effectiveness, or performance of a product or clinical study material and/or its packaging components after it is has been released for distribution to an end customer that affects the performance of such product.

- The pharmacist or other designated individual will maintain records of study intervention delivered to the study site, the inventory at the study site, the distribution to and use by each participant, and the return of materials to the Sponsor for storage or disposal/destruction of materials at the study site. These records should include dates, quantities, batch/serial numbers, expiration dates, in-clinic temperature log, and unique code numbers assigned to the study intervention and study participants.
- The Investigator will maintain records that adequately document that the participants were administered the correct study treatment kits and reconcile the products received from the drug dispensing center. Investigational product will not be returned to the Sponsor or disposed of until accountability has been fully monitored.

Further guidance regarding preparation, handling, storage, and accountability and information for the final disposition of unused study intervention is provided in the Pharmacy Manual.

# 6.3. Measures to Minimize Bias: Randomization and Blinding

### 6.3.1. Randomization

All participants will be randomized on Day 1 in a ratio of 2:1:2 to ALXN2050 180 mg bid, ALXN2050 120 mg bid, or placebo, using a centralized IRT after the Investigator has verified that they are eligible to participate in the study (Section 4.1).

### 6.3.2. Blinding

All investigational site personnel, Alexion staff/designees, other staff directly associated with the conduct of the study, and all participants will be blinded to the treatment assignment during the PEP. The double-blind will be maintained by using identical study treatment kits and labels for all participants. The placebo tablet will have an identical appearance to that of ALXN2050. The randomization code will be maintained by the IRT provider. Select Alexion staff will be unblinded for the analyses of the PEP and will remain unblinded during the ETP and OLE. All participants, Investigators, and site personnel will remain blinded to treatment assignment from Day 1 through the end of the ETP (ie, Week 34). During the ETP, participants, Investigators, and site personnel will continue to be blinded to the actual dose received until an optimal dose is chosen (if this occurs during the study). If an optimal dose is chosen, then all participants, Investigators, and site personnel will be moved to that dose, and participants, Investigators, and site personnel will no longer be blinded to treatment assignment/dose.

In case of an emergency, the Investigator has the sole responsibility for determining if unblinding of a participant's intervention assignment is warranted. Participant safety must always be the first consideration in making such a determination. If the Investigator decides that unblinding is warranted, the Investigator will be able to unblind the participant's treatment allocation directly using the IRT. If a participant's intervention assignment is unblinded, Alexion or designee must be notified within 24 hours after breaking the blind. The date and reason that the blind was broken must be recorded in the source documentation and case report form (CRF), as applicable.

In the event of a suspected unexpected serious adverse reaction (SUSAR), follow reporting guidance in Section 8.3.4. The blind will be maintained for persons responsible for the ongoing conduct of the study (eg, Monitors, Investigators) and those responsible for data analysis and interpretation of results, such as biometrics personnel.

Unblinded information will only be accessible to those who are involved in safety reporting to Health Authorities, Independent Ethics Committees (IECs), and/or Institutional Review Boards (IRBs).

Investigators will receive only blinded information unless unblinded information is judged necessary for safety reasons.

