- Extended Treatment Period of 26 weeks (Week 8 to Week 34) The ETP begins at the Day 57 (Week 8) Visit after all assessments of the visit are performed, but before the administration of ALXN2050 in the clinic and postdose PK/PD sampling. During this timeframe, participants in the ALXN2050 180 mg bid and ALXN2050 120 mg bid groups will continue taking the dose to which they are randomized. Participants in the placebo group will be stratified by MG-ADL total score at baseline (pre-placebo) and re-randomized in a 1:1 ratio to either ALXN2050 180 mg bid (Group 3a) or ALXN2050 120 mg bid (Group 3b). All participants will receive active study intervention; however, the actual dosage of ALXN2050 will be blinded to participants, Investigators, and site personnel. Visits at Weeks 9, 10, 11, 13, 14, and 15 will be conducted via telephone contact (Table 3). Participants will present for in-clinic visits at Weeks 12, 16, 26, and 34. The first dose of study intervention during in-clinic visit days will be administered by the site personnel. The participant will take the second dose of study intervention at home. The last visit for the ETP will be the Week 34 Visit.
- Open-label Extension Period of up to approximately 1.5 years (Week 34 to Week 117) – The OLE Period begins at the Day 239 (Week 34) Visit after all assessments of the visit are performed, but before the administration of ALXN2050 in the clinic and postdose pharmacokinetics/pharmacodynamics (PK/PD) sampling. During this timeframe, all participants will receive active study intervention. If an optimal dose of ALXN2050 has been identified, all participants will be switched to this optimal dose, as long they have completed the first 34 weeks of treatment. However, the actual dose of ALXN2050 will continue to be blinded to participants, Investigators, and site personnel during this study period until they are switched to the

optimal dose, if one is identified during the study. Participants will return to the clinic approximately every 3 months as indicated in the SoA (Table 4). The first dose of study intervention during in-clinic visit days will be administered by the site personnel. The participant will take the second dose of study intervention at home. The last visit for the OLE Period is the EOS Visit.

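### Protocol 6.3.2 lets the dose blind end, and moves participants, during the ETP once a dose is chosen; this contradicts its own Week 34 sentence and the 34-week switching rule stated elsewhere

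*Protocol*

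**What the plan says.** The first paragraph of Protocol 6.3.2 ends with three statements about participants, Investigators and site personnel:

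- A. They "will remain blinded to treatment assignment from Day 1 through the end of the ETP (ie, Week 34").
- B. During the ETP they "will continue to be blinded to the actual dose received until an optimal dose is chosen", if that happens during the study.
- C. "If an optimal dose is chosen, then all participants, Investigators, and site personnel will be moved to that dose". The same sentence goes on to end the blind: "participants, Investigators, and site personnel will no longer be blinded to treatment assignment/dose".

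Protocol 4.1 describes the same periods differently. For the ETP it says that "the actual dosage of ALXN2050 will be blinded to participants, Investigators, and site personnel", with no exception for a dose decision, and Groups 1 and 2 stay on their randomized dose. The switch belongs to the OLE: "all participants will be switched to this optimal dose, as long they have completed the first 34 weeks of treatment". The dose blind in the OLE "will continue to be blinded to participants, Investigators, and site personnel during this study period until they are switched".

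Protocol 6.6, the Synopsis (Overall Design) and SAP 1.2 cover switching but not blinding. All three limit the switch to participants who have reached 34 weeks. Section 6.6 adds that only those not already on the chosen dose are switched, and it bars dose changes for individual participants.

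**The concern.** Section 6.3.2 is where site staff and whoever builds the release rules would look to learn when the blind ends. Statement A fixes that point at Week 34. Statements B and C tie it to an event that can come earlier, and C attaches no minimum time on treatment to the move.

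The triggering event was planned for. Selecting a dosage is a stated goal in Protocol 9.2, and the first data lock in Protocol 9.5.1 comes when the last randomized participant has only just finished Week 8. If a dose were picked soon after that lock and 6.3.2 were applied literally, some participants would lose the dose blind in the ETP and some would change dose before Week 34. MG-ADL is participant-reported, and MGFA-PIS, Clinical Deterioration and adverse event causality involve Investigator judgment, so knowledge of dose could influence them. Early switching would also mix doses within Groups 1, 2, 3a and 3b.

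**Working it through.** The plan has no figure to reproduce here. The check compares the texts and adds the period arithmetic.

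**1. Side by side**

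| Place | When the dose blind ends | Who changes dose, and when |
|---|---|---|
| 6.3.2, statement A | Not before Week 34 | Not addressed |
| 6.3.2, statements B and C | When a dose is chosen, including during the ETP | Everyone, on the choice; no 34-week condition |
| 4.1, ETP | Not during the ETP | Groups 1 and 2 stay on their randomized dose |
| 4.1, OLE | At the switch | After 34 weeks |
| 6.6 | Not addressed | After 34 weeks, if not already on the chosen dose |
| Synopsis; SAP 1.2 | Not addressed for this switch | In the OLE, after 34 weeks |

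Statements B and C conflict with A and 4.1 on blinding. Statement C conflicts with 4.1, 6.6, the Synopsis and SAP 1.2 on switching.

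**2. Can the texts be reconciled?** One could read A as protecting treatment assignment and B as releasing only dose. That fails, because C releases both and 4.1 explicitly blinds the dosage in the ETP.

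**3. When would the conflict matter?** The PEP is 8 weeks and the ETP 26, so 8 + 26 = Week 34. Week 34 is Day 34 × 7 + 1 = 239, as in the Schedule of Activities. At the first lock the last participant is at Week 8, with 34 − 8 = 26 ETP weeks left. If the dose is chosen *d* weeks after the last Week 8 visit, that participant is at Week 8 + *d*:

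- *d* < 26: at least that participant, if still on study, is in the ETP.
- *d* = 8: everyone still on study has reached Week 16, so only the Week 26 and Week 34 visits and later events are exposed.
- *d* ≥ 26, which includes any choice after the second lock (last participant's Week 34 visit): nobody is exposed.

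The optional early interim in Protocol 9.5 is not a trigger, because it is stated to have no effect on the progress of the study.

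**4. What would be revealed, and who would switch?** By the ETP everyone takes active drug, since placebo participants are "re-randomized in a 1:1 ratio to either ALXN2050 180 mg bid (Group 3a) or ALXN2050 120 mg bid (Group 3b"). The blind at issue is 180 mg versus 120 mg. Under the planned 2:1:2 allocation, and assuming no differential dropout, the ETP split is:

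- 180 mg: 2/5 + (1/2 × 2/5) = 3/5 = 60%
- 120 mg: 1/5 + (1/2 × 2/5) = 2/5 = 40%

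Of those exposed, about 40% would be switched early if 180 mg were chosen, and about 60% if 120 mg were chosen.

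**5. Which analyses?** All Week 8 visits precede the first lock, so the primary and secondary endpoints are outside the exposed period. What remains is Week 8 to 34 efficacy, for which SAP 5.5 plans no formal testing, and safety summaries, for which SAP 5.6 plans none either. SAP 5.6.2.2 also tabulates adverse events by the dose taken at the time, which partly handles mixed doses.

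**The case against.** The strongest reply is that this is a drafting slip with no practical consequence. The switching rule is stated consistently in four places, and 6.6 is the operative section on dose changes. Statement C also says that Investigators and site personnel will be moved to the dose, so it is visibly garbled and could not be executed literally. The SAP Addendum records that the study was terminated for lack of efficacy after the Week 8 analysis, and it drops all exploratory analyses. No choice of an optimal dose is documented. Most of this stands: the ETP reference in B is probably a slip for the OLE, and the realized effect looks small. It does not make the text correct, because 4.1 and 6.3.2 give different answers on when the blind ends.

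Four stronger readings are tempting and are not supported:

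- *The sponsor intended to unblind during the ETP.* Statement A, 4.1, 6.6, the Synopsis and SAP 1.2 all point the other way.
- *The placebo comparison is compromised.* All participants are on active drug by then, and Week 8 data are already collected. Releasing assignments would only tell Groups 3a and 3b, after the fact, that they started on placebo.
- *A definite number would be unblinded.* Under uniform accrual over *A* weeks and no dropout, the share still in the ETP is max(0, 26 − *d*)/*A*. With *d* = 8, *A* = 52 gives 18/52 = 35% (24 of 70) and *A* = 130 gives 18/130 = 14% (10 of 70). The documents give neither accrual duration nor decision date, nor which analysis selects the dose. These figures are illustrations of assumptions, not findings.
- *Participants already on the chosen dose currently have no end to their blind.* As things stand, statement C supplies one. The gap would appear only if 6.3.2 were made to copy 4.1, which ends the blind at a switch that 6.6 does not give these participants.

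**Conclusion.** The contradiction is real, and the last two sentences of that 6.3.2 paragraph are wrong as written. It is a minor wording error, not a design choice.

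Harm would require two conditions: that 6.3.2 is followed literally, and that a dose is chosen before the last participant's Week 34 visit. Participants still in the ETP would then be unblinded to 180 mg versus 120 mg, and those not on the chosen dose would be switched early. The effect would be confined to descriptive post-Week 8 efficacy and safety summaries. The number exposed cannot be derived from the documents, it is zero if the choice follows the Week 34 lock, and no bias is estimated.

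Under the SAP Addendum, the outputs that could still carry the problem are the exposure and adverse event summaries by Group 1, 2, 3a and 3b, and the MG-ADL and QMG tables across all visits. Nothing in the documents shows that the trigger occurred.

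**What to change.** In Protocol 6.3.2, change *During the ETP* to *During the OLE Period* in statement B, and replace the last sentence of the paragraph with:

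> If an optimal dose is chosen, participants who have completed 34 weeks of treatment and are not already receiving it will be switched to that dose. Once a participant has completed 34 weeks and has been switched or confirmed as already receiving the optimal dose, the participant, Investigator and site personnel will no longer be blinded to that participant's treatment assignment/dose. Assignments of participants still in the ETP are not released.

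This keeps the existing release of treatment assignment as well as dose, and gives an end point to participants who do not need to switch. Align the closing words of the OLE blinding sentence in 4.1, which tie the end of the blind to the switch alone.

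The cost is two edits in 6.3.2 and one in 4.1. The IRT release rule should match; its specification is not in the documents. The downside is that a site may hold blinded and unblinded participants at the same time for up to 26 weeks (34 − 8) if a dose is chosen at the first lock.
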